22.6 SECONDARY ENDPOINTS

Secondary endpoints will be described in the SAP and will include:

- Immunological Response 2: Reduction from baseline in the % of aberrant IELs vs intestinal epithelial cells
- Histological Response: improvement from baseline in small intestinal VH:CD ratio score, Marsh score and total IEL counts
 - VH:CD ratio by validated morphometry. Includes the % of patients with histological remission (VH:CD > 2).
 - Marsh-Oberhuber classes, Marsh 0, 1, 2, 3a-c. Grouping by converting the morphometric results into Marsh classes (Mäki-Jilab converter). Includes the % of patients with histological remission (Marsh 0-1).
 - IEL: for mucosal inflammation the density of IELs/100 epithelial cells will be calculated. The analysis will also include the percentage of patients with normalization of IEL counts vs. epithelial cells (% IELs < 50%).

- Clinical response: change from baseline in symptoms,
 - BSFS and number bowel movements by day and week
 - GSRS and CeD-GSRS, by week

In general, efficacy measures which require pre- and post-treatment biopsies will be based on the PP population (at least 2 biopsies, the second at least on Week 6 or later). Continuous variables will be analyzed based on the ITT population.

Change from baseline of Immunological Response 2, VH:CD and of total IEL counts will be analyzed using the same method as for the primary endpoint.

The Marsh scores will be analyzed using a multinomial logistic regression model, where treatment group, baseline Marsh score, and a treatment group-by-baseline Marsh score interaction term will be included in the model.

The secondary variable BSFS will be analyzed by calculating daily and weekly number and type of bowel movements. The bowel movement counts will be analyzed using generalized linear mixed models with subject as random effect. The statistical model will also include treatment group, time (week) and their interaction. The change in the weekly BSFS scores will mainly be assessed with descriptive statistics, where change from the 'normal (mid-scale)' will be explored. The GSRS and the CeD-GSRS will be analyzed using a linear mixed effects repeated measures model (MMRM) with the baseline value, treatment group, time point and a time point-by-treatment group interaction term as fixed effects with an underlying correlation structure between the time points that results in the best fit for the model. Subject will be included as a random effect.

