The secondary endpoints Immunological Response 2, VH:CD ratio, Marsh score and total IEL counts will be evaluated by the change from baseline to Week 12 between the AMG 714 dose arm and the placebo arm. BSFS, GSRs and CeD-GSRs will be evaluated by comparing the change from baseline in weekly scores of AMG 714 dose arm and placebo arm.

For the purpose of this study, and in agreement with leading experts in RCD-II (Malamut *et al*, 2010; Nijeboer *et al*, 2015a, 2015b), aberrant IELs will be defined by flow cytometry as surface CD3-negative, intra-cellular CD3-positive IELs (sCD3-, icCD3+). The cut-off chosen for diagnosis of RCD-II is 20% in accordance with most recent studies (Nijeboer *et al*, 2015b). In IHC, these cells are identified as icCD3+, sCD8- and the cut-off is 50% (Nijeboer *et al*, 2015b).

In addition to this standard definition of aberrant IEL (what can be called “classic RCD-II”), it is not uncommon to observe the diagnosis of RCD-II in subjects with an atypical flow cytometric phenotype of the aberrant IELs, yet otherwise meeting the definition of RCD-II. These “Atypical RCD-II” patients may be enrolled in the study and would be part of the intent-to-treat (ITT) population as well as of the per protocol (PP) population except for the analysis of Immunological Response 1 and 2 (since the aberrant cells object of Immunological Response endpoints are different). In other words, all endpoints except Immunological Response 1 and 2 will be assessed with inclusion of any atypical subject enrolled. However, because it is possible that these patients behave differently, sensitivity analyses may also be conducted excluding the atypical subjects.

The **secondary objective** of the study is:

- To assess the safety and tolerability of AMG 714 when administered to adult patients with RCD-II.

The **safety endpoints** of the study are:

- Adverse events (AEs);
- Clinical laboratory tests;
- Physical examination;
- Vital signs;
- Immunogenicity.

Clinical laboratory tests -including immunogenicity-, physical examinations and vital signs will be tabulated by time point and treatment group and reviewed for potential safety signals. All adverse events (AEs) and serious adverse events (SAEs) will be listed and tabulated by system organ class (SOC), preferred term (PT) and further by severity and relatedness to the study drug.

The **exploratory objectives** of the study are:

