8.2.1 Definition of derived variables

Geometric mean will be calculated as:

$$\text{mean}_{\text{geo}} = \exp\left\{\frac{1}{n} \sum_{i=1}^n \ln x_i\right\}.$$

Values that are missing or not available will be ignored in calculation of geometric mean.

CV%_{geo} will be calculated using the following formula:

$$\text{CV}\%_{\text{geo}} = 100\% \cdot \sqrt{\exp V_{\ln} - 1}.$$

Values that are missing or not available will be ignored in calculation of CV%_{geo}.

Absolute change from baseline for a given treatment needs to be calculated, the following formula will be used:

$$\text{Absolute change from baseline} = \text{Post-baseline value} - \text{Pre-dose value}.$$

For weekly scores, Week 0 score is considered to be the baseline value. If Week 0 score is not available, the first non-missing result within 2 weeks of treatment will be used as baseline. For daily scores (e.g. CeD PRO), Day 0 score is considered to be the baseline; in case Day 0 score is not available, the first non-missing result within 2 weeks of treatment will be used as baseline. Otherwise, the given subject will be considered non-evaluable for the specific test. In case pre-dose value doesn't exist (i.e. for biopsy endpoints), screening value will be used as baseline.

In the case where relative (%) change from baseline needs to be calculated, the following formula will be used:

$$\text{Relative (\%) change from baseline} = (\text{Post-baseline value} - \text{Pre-dose value}) / (\text{Pre-dose value}) \cdot 100\%.$$

For weekly scores, Week 0 score is considered to be the baseline value. If Week 0 score is not available, the first non-missing result within 2 weeks of treatment will be used as baseline. For daily scores (e.g. CeD PRO), Day 0 score is considered to be the baseline; in case Day 0 score is not available, the first non-missing result within 2 weeks of treatment will be used as baseline. Otherwise, the given subject will be considered non-evaluable for the specific test. In case pre-dose value doesn't exist (i.e. for biopsy endpoints), screening value will be used as baseline.

Body mass index (BMI) is calculated using the formula:

$$\text{BMI (kg/m}^2\text{)} = \text{weight (kg)} / [\text{height (m)} * \text{height (m)}].$$

Body surface area (BSA) is calculated using Dubois' formula:

$$\text{BSA (m}^2\text{)} = 0.007184 * \text{height (cm)}^{0.725} * \text{weight (kg)}^{0.425}.$$

Table 2 Decimal places for summary statistics of continuous and categorical variables

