The modelling results (ANOVA table, parameter estimates, estimated treatment effect, marginal means estimates and results of the check of assumptions) will be tabulated and 95% confidence intervals added, where appropriate.

As a secondary assessment, the same model will be fitted using the absolute change in total IEL counts as a response variable. The modelling results (ANOVA table, parameter estimates, estimated treatment effect, marginal (i.e. least squares) means estimates and results of the check of assumptions) will be tabulated and 95% confidence intervals added, where appropriate.

The baseline and post-baseline values along with the change from baseline values both relative and absolute) will also be described by summary statistics and tabulated by treatment group. Baseline and post baseline values will also be listed.

PP population will be used for the analysis.

Change from baseline in clinical symptoms: Bristol Stool Form Scale (BSFS)

The Bristol Stool Form Scale is a pictorial aid to help subjects identify the shape and consistency of their bowel movements during the study (Riegler *et al* 2001).

Subjects will be asked to complete this form daily using an electronic diary at the time of each bowel movement from randomization through the Final Study Visit (Visit 9; Week 16/Day 112). If no bowel movements were experienced by the subject on any given day, the subject should document this using the electronic diary.

BSFS will be described by calculating daily and weekly number and type of bowel movements.

The total weekly bowel movement counts will be analysed using generalized linear mixed models with subject as a random effect. The statistical model will include as fixed effects treatment group, time (week) and their interaction. Poisson distribution with log-link will be used for modelling the counts. The following model will be fitted:

$$\log(Y_{ijk}) = \mu + \alpha_j + \gamma_k + \lambda_{jk} + \eta_i + \varepsilon_{ijk},$$

where

- Y_{ijk} is the bowel movement count for subject i ($i = 1, \dots, n_j$) from treatment group j ($j = 1, 2$) at week k ($k = 0, 1, \dots, 16$),
- μ is the overall mean on log-scale,
- α_j is the fixed effect due to treatment j on log-scale,
- γ_k is the fixed effect due to week k on log-scale,
- λ_{jk} is the fixed interaction effect due to treatment j and week k on log-scale,

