Weekly bowel movements and their BSFS types will be tabulated by treatment group and week and summarized by descriptive statistics, absolute numbers and percentages. Also, percentage of subjects with diarrhoea (at least 1 BSFS ≥ 6 for the week) and percentage of subjects with constipation (at least 3 days without bowel movement for the week) by week and by treatment group will be presented. Mean weekly bowel movement counts will also be presented graphically by time point and treatment group.

As an exploratory assessment, averages by treatment for proportion of subjects showing BSSF ≥ 6 by time will be plotted. The differences in treatment AUCs will be explored using one-way analysis of variance. These analyses will be conducted internally by Celimmune.

The daily bowel movement counts and their BSFS scores will only be listed.

ITT population will be used for the analysis as long as there is a baseline and post-treatment measure (i.e. not lost to follow-up).

Change from baseline in clinical symptoms: Gastrointestinal Symptom Rating Scale (GSRs)

The GSRs is a 15-question 7-scale questionnaire used to assess five dimensions of gastrointestinal syndromes: diarrhea, indigestion, constipation, abdominal pain and reflux (Svedlund *et al* 1988). While not specific for celiac disease, the GSRs is widely used in gastroenterology and has been used in several clinical trials of experimental medications in celiac disease, thus becoming a very useful tool with abundant existing reference data (Kelly *et al* 2013; Lähdeaho *et al*, 2011; Leffler *et al*, 2015).

Subjects will be asked to complete this questionnaire weekly, using an electronic diary, from the day of randomization through the Final Study Visit (i.e. on Visits 1 to 9).

The total GSRs score will be calculated as the mean of the scores of all 15 questions, with the scores for the individual questions between 1 (No discomfort at all) and 7 (Very severe discomfort). Therefore, the smaller the total GSRs score, the milder the symptoms of the subject.

The change from baseline in total GSRs score will be analysed using a linear mixed effects repeated measures model (MMRM) with the baseline value, treatment group, time point and a time point-by-treatment group interaction term as fixed effects with an underlying correlation structure between the time points that results in the best fit for the model. Subject will be included as a random effect. The following model will be fitted:

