β is the parameter estimate of the baseline total CeD PRO score,

γ is the parameter estimate of day,

λ_{jk} is the fixed interaction effect due to treatment j and day k ,

η_i is the random effect due to subject i ,

ε_{ijk} is the random error for subject i from treatment group j for day k .

Note that the proper functional form of the time (day) will be explored, e.g. square of day might be added.

The following SAS program will be used for carrying out the daily level analysis:

```
proc glimmix data=cedpro_d;
  class subjid trt;
  model cedpro_d = cedpro_d_bl trt day trt*day / solution;
  random _residual_ / subject=subjid type=AR(1);
```

```
estimate "AMG 714 vs Placebo" trt 1 -1 /alpha=0.05 cl;  
lsmeans trt /alpha=0.05 cl;  
ods output CovParms=Cov_Par LSMeans=LS_est Estimates=Eff_est  
FitStatistics=Fit_Stat ParameterEstimates=Par_est  
Tests3=Type_3;  
  
run;
```

For the weekly level data, the following model will be fitted:

$$Y_{ijk} = \mu + \alpha_j + \gamma_k + \lambda_{jk} + \beta \cdot \text{baseline CeD PRO}_{ij} + \eta_i + \varepsilon_{ijk},$$

where

Y_{ijk} is the total CeD PRO score for subject i ($i = 1, \dots, n_j$) from treatment group j ($j = 1, 2$) at week k ($k = 0, 1, \dots, 16$),

μ is the overall mean,

α_j is the fixed effect due to treatment j ,

γ_k is the fixed effect due to week k ,

λ_{jk} is the fixed interaction effect due to treatment j and week k ,

β is the parameter estimate of the baseline total CeD PRO score,

η_i is the random effect due to subject i ,

ε_{ijk} is the random error for subject i from treatment group j for week k .

The following SAS program will be used for carrying out the weekly level analysis:

```
proc glimmix data=cedpro_w;  
class subjid trt week (ref=FIRST);  
model cedpro_w = cedpro_w_bl trt week trt*week / solution;  
random _residual_ / subject=subjid type=AR(1);  
estimate "AMG 714 vs Placebo" trt 1 -1 /alpha=0.05 cl;  
estimate "Week 0: AMG 714 vs Placebo" trt 1 -1  
trt*week 0 0 0 0 0 0 0 0 0 0 0 0 0 0 0 0 0 1  
0 0 0 0 0 0 0 0 0 0 0 0 0 0 0 0 0 -1 /alpha=0.05 cl;  
estimate "Week 1: AMG 714 vs Placebo" trt 1 -1  
trt*week 1 0 0 0 0 0 0 0 0 0 0 0 0 0 0 0 0 0  
-1 0 0 0 0 0 0 0 0 0 0 0 0 0 0 0 0 0 /alpha=0.05 cl;  
...  
estimate "Week 16: AMG 714 vs Placebo" trt 1 -1  
trt*week 0 0 0 0 0 0 0 0 0 0 0 0 0 0 0 0 1 0  
0 0 0 0 0 0 0 0 0 0 0 0 0 0 0 0 -1 0 /alpha=0.05 cl;  
lsmeans trt /alpha=0.05 cl;  
lsmeans trt*week /alpha=0.05 cl;  

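### The BSFS bowel-movement model has no baseline term and treats Week 0 as an outcome although the endpoint is change from baseline, and the weekly CeD PRO model uses Week 0 as both covariate and outcome

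*SAP*

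**What the plan says.** - **Endpoint.** SAP 2: "BSFS, GSRs and CeD-GSRs will be evaluated by comparing the change from baseline in weekly scores of AMG 714 dose arm and placebo arm". SAP 8.2.1: "For weekly scores, Week 0 score is considered to be the baseline value".
- **Bowel-movement model.** SAP 8.6.2 fits a Poisson mixed model with log link and a random subject effect to the weekly count, indexed from Week 0 to Week 16. Its fixed part is "The statistical model will include as fixed effects treatment group, time (week) and their interaction". Protocol 22.6 lists the same terms: "The statistical model will also include treatment group, time (week) and their interaction". Neither names a baseline covariate. The SAP still requires a baseline measure before a subject enters the BSFS analysis.
- **Sister endpoints.** GSRS and CeD-GSRS (SAP 8.6.2) are modelled as change from baseline, starting at Week 1, "with the baseline value, treatment group, time point and a time point-by-treatment group interaction term as fixed effects".
- **CeD PRO.** The weekly model in SAP 8.7.6 is indexed from Week 0, has an explicit Week 0 arm contrast, and also carries the baseline score: "model cedpro_w = cedpro_w_bl trt week trt*week / solution". The daily model is indexed from Day 0 and likewise has the baseline score as a covariate.
- **When the diary starts.** Protocol 11.2.2 hands out the e-diary at Visit 1, the first dosing day. SAP 8.6.2 starts BSFS recording at randomization. If the Week 0 score is missing, SAP 8.2.1 takes the first result within 2 weeks of treatment.

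**The concern.** A model of raw counts with no baseline term compares how many bowel movements each arm has, not how far each arm has moved. With 8 placebo subjects and no stratification, the arms may differ at Week 0 by chance, and part of that difference then shows up as a treatment effect or hides one. Week 0 also enters any average over weeks, although little or no effect can be present there. At stake are the precision and interpretation of a secondary clinical endpoint, and its consistency with the GSRS analyses in the same family. CeD PRO has a related slip: a Week 0 row conditioned on itself carries no treatment information but still counts in the overall contrast.

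**Working it through.** **1. Plan's own figure.** The documents give no power, effect, variance or correlation for stool counts. For the primary endpoint (SAP 7), the noncentrality is 20 / (17.4 x sqrt(1/16 + 1/8)) = 20 / (17.4 x 0.433) = 2.65. With 22 df and two-sided alpha 0.10, power is 82.3%, which agrees with the stated figure of at least about 80%. The same 16/8 layout is used below, with two-sided 0.05 for secondary tests (SAP 8.2).

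**2. What the contrasts estimate.** Let D_k be the arm difference in log mean count at week k: the treatment effect plus the treatment-by-week term.
- Per-week arm contrast: D_k, a difference in level.
- Overall contrast: the mean of D_0 to D_16. If D_0 = 0 and D_k = d afterwards, this is 16d/17, a dilution of 1/17 = 5.9%.
- Change from baseline: D_k - D_0. The model can produce it, but the readable text does not name it.

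**3. Size of a chance imbalance (assumed SDs).** A one-SD arm difference in subject log rate is s x 0.433. For s = 0.4 this is 0.173, a rate ratio of 1.19. For s = 0.6 it is 0.260, a rate ratio of 1.30. In simulation, about 0.3 to 0.65 of an observed Week 0 difference carried into a single-week contrast, roughly the week-to-week correlation. Type I error was 0.046-0.056.

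**4. Power, 12-week average.** Assumptions: 14 movements per week, true rate ratio 0.70 (log 0.357), between-subject log SD s, weekly log SD w, and an untreated Week 0. Per-week variance is v = w^2 + 1/14. Per-subject variances are:
- unadjusted, U = s^2 + v/12
- baseline-adjusted, A = U - s^4/(s^2 + v)
- change against Week 0, C = v + v/12

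Each SE is 0.433 x the square root of the variance. Power for U and A is from simulation of Poisson counts, analysed on subject log means rather than by the full mixed model.

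| s, w | U / A / C | SE: U / A / C | Power: U vs A | Relative loss |
|---|---|---|---|---|
| 0.20, 0.30 | 0.053 / 0.046 / 0.175 | 0.100 / 0.092 / 0.181 | 91% vs 94% | 3% |
| 0.25, 0.30 | 0.076 / 0.059 / 0.175 | 0.119 / 0.105 / 0.181 | 81% vs 89% | 9% |
| 0.30, 0.30 | 0.103 / 0.071 / 0.175 | 0.139 / 0.116 / 0.181 | 67% vs 80% | 16% |
| 0.40, 0.25 | 0.171 / 0.084 / 0.145 | 0.179 / 0.126 / 0.165 | 49% vs 73% | 33% |
| 0.50, 0.30 | 0.263 / 0.112 / 0.175 | 0.222 / 0.145 / 0.181 | 34% vs 61% | 44% |
| 0.60, 0.30 | 0.373 / 0.125 / 0.175 | 0.265 / 0.153 / 0.181 | 24% vs 55% | 56% |

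For s = 0.4-0.6, the change contrast reached 40-51% in simulation. A is the smallest variance in every row.

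**5. Single-week contrast.** With correlation r between Week 0 and the later week, the relative variances are 1 (unadjusted), 1 - r^2 (adjusted) and 2(1 - r) (change). With the effect set so that the adjusted analysis has 80% power:

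| r | Unadjusted | Relative loss | Change vs Week 0 |
|---|---|---|---|
| 0.3 | 76% | 5% | not reported |
| 0.5 | 68% | 15% | 68% |
| 0.7 | 52% | 35% | 74% |
| 0.8 | 39% | 51% | 76% |
| 0.9 | 23% | 71% | 78% |

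**6. CeD PRO.** For a true effect of 0.80, the overall contrast with the Week 0 row included should be 0.80 x 16/17 = 0.75. A REML simulation gave 0.74 with that row and 0.79 without it.

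**7. If Week 0 is partly post-dose.** Suppose the Week 0 count already carries half the effect. The baseline slope is b = s^2/(s^2 + v), which is 0.16/0.294 = 0.54 at s = 0.4 and 0.36/0.521 = 0.69 at s = 0.6. The adjusted log effect becomes 0.357 x (1 - b/2), so the rate ratio moves from 0.70 to about 0.77 and 0.79. Simulation gave 0.76-0.79, with adjusted power of 28-47% against 25-49% unadjusted. The gain is then lost.

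**The case against.** - **The test is not visible.** The readable SAP text stops partway through the BSFS model definition, so its code and contrasts cannot be seen. That gap is not an error in the plan. With Week 0 in the response, the treatment-by-week terms against Week 0 do estimate change. A reader might infer that the model cannot address its endpoint. The documents do not support that: what is established is that no change contrast is named in the readable text. The parallel weekly CeD PRO code requests only overall and per-week arm contrasts, though its coefficient output could contain contrasts against Week 0.
- **The power loss rests on assumptions.** This stands. A reader might infer a fixed loss of a third to two thirds. No stool-count variance or correlation is given, and with small between-subject spread the loss is only a few per cent.
- **Adjustment can do harm.** This also stands. No pre-dose diary week is collected, and SAP 8.2.1 permits a baseline from up to 2 weeks into treatment. The fix must deal with this.
- **Stakes are limited.** This is a secondary endpoint in an exploratory trial, type I error is intact, and weekly counts are tabulated and plotted by arm, so an imbalance would be seen. Seeing it does not correct the estimate.

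**Conclusion.** The concern holds as a mismatch between endpoint and model. The BSFS model has no baseline term and includes Week 0 as an outcome, while the endpoint is change from baseline and the sister models adjust for it. Level contrasts carry part of any Week 0 imbalance, and an average over Weeks 0-16 loses 1/17 of the effect. Validity is not at issue.

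For the 12-week average, and assuming an untreated Week 0, the relative power loss is roughly one third to a little over one half at between-subject log SD 0.4-0.6 (weekly SD 0.25-0.30), and about 3-16% at 0.2-0.3 (weekly SD 0.30). A change contrast against Week 0 answers the right question but is less efficient than baseline adjustment at these SDs. The CeD PRO overlap understates the overall weekly contrast by about 6% and leaves the per-week contrasts available; the daily model has the same overlap at Day 0. The change should be made, but it is not critical to the trial's primary conclusion.

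**What to change.** **BSFS**
1. State which days form Week 0, using pre-dose or the earliest available data, and state the limits of that window. Do not use a count from up to 2 weeks after dosing as the baseline for this model.
2. Name the contrast that tests change from baseline.
3. Either model Weeks 1-16 with log(baseline count + 0.5) as a covariate, or keep Week 0 as an outcome with the arms constrained equal there.

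**CeD PRO**

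Remove Week 0 (weekly model) and Day 0 (daily model) from the outcome rows and keep them only as the covariate.

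**Cost**

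SAP wording, with Protocol 22.6 reconciled, and one degree of freedom. The downside is that if the Week 0 count includes post-dose days, adjustment can absorb some early treatment effect. The equal-arms constraint is open to the same objection. A true pre-dose diary week would avoid it, but that is new data collection and not a wording change.

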13.3.1 Bristol Stool Form Test

The Bristol Stool Form Scale (BSFS, Appendix C) is a pictorial aid to help subjects identify the shape and consistency of their bowel movements during the study (Riegler *et al* 2001).

Subjects will be asked to complete this form daily using an electronic diary at the time of each bowel movement from randomization through the Final Study Visit (Visit 9; Week 16/Day 112). If no bowel movements were experienced by the subject on any given day, the subject should document this using the electronic diary.

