22.3 MISSING DATA

Subjects withdrawing from study drug administration before Week 6 will be excluded from the PP analysis and the second biopsy will not be collected. Subjects withdrawing on or after Week 6 will be included and the second biopsy will be collected. Missing data after Week 6 will be imputed and the imputation rules will be described in the SAP.

No other data imputation will be done.

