8.2.2 Missing values

If a discontinuation occurs on or after Week 6 and the second biopsy is collected then the subject is considered evaluable, the results of the second biopsy (pre-maturely done before Week 12) will be used to investigate the change from baseline to Week 12, i.e. the values of parameters obtained from this biopsy will be carried forward for Week 12 efficacy assessments (LOCF). This LOCF will only be done for PP population and only for variables depending on the biopsy.

AMG 714 concentrations below the lower limit of quantification (LLOQ) will be assigned a value of 0.5 x LLOQ in mean calculations for the summary of AMG 714 concentrations. A similar rule will be used for any other assay results below the LLOQ. All assay results over the upper limit of quantification (ULOQ) will be assigned a value of ULOQ.

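### Weekly bowel-movement totals are modelled without adjusting for the number of diary days recorded, so short or partly recorded weeks count as fewer movements

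*SAP*

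**What the plan says.** SAP 8.6.2 (Bristol Stool Form Scale) states: "The total weekly bowel movement counts will be analysed using generalized linear mixed models with subject as a random effect". It continues: "The statistical model will include as fixed effects treatment group, time (week) and their interaction". On the distribution it says: "Poisson distribution with log-link will be used for modelling the counts". The equation indexes weeks from k = 0 to 16, so Week 0 is one of the responses and not a covariate. The terms are an overall mean, treatment, week, their interaction, a subject effect and a subject-by-week error term. There is no exposure term.

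Protocol 13.3.1 tells subjects how to handle days without a movement: "If no bowel movements were experienced by the subject on any given day, the subject should document this using the electronic diary". An empty day that was documented can therefore be told apart from a day that was not recorded.

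On missing data, Protocol 22.3 leaves imputation after Week 6 to the SAP and adds: "No other data imputation will be done". SAP 8.2.2 supplies only a carry-forward rule for biopsy results: "This LOCF will only be done for PP population and only for variables depending on the biopsy". SAP 8.2.1 gives a substitute when the Week 0 score is unavailable, but no rule for a week that was partly recorded. The analysis set is described as "ITT population will be used for the analysis as long as there is a baseline and post-treatment measure".

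In the text supplied for review, the bowel-movement section breaks off after the definition of the interaction term. The definition of the error term and the SAS code cannot be read.

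**The concern.** A sum over a week depends on how many days were observed. If a subject records 5 days, the model sees a lower count and has no means of knowing that two days are absent. A subject who stops mid-week, or whose last visit falls early, likewise contributes a short week that is read as a low rate.

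The SAP avoids this elsewhere: under SAP 8.7.6 the weekly CeD PRO score is the mean of the daily totals, which adjusts for recorded days. The bowel-movement total does not.

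The secondary point is the variance. A Poisson model with only a subject intercept sets the within-subject variance equal to the mean. If stool counts vary more than that from week to week, and nothing else in the fitted model absorbs it, contrasts between weeks get standard errors that are too small. Those contrasts matter here because the endpoint is change from baseline and Week 0 enters as a response.

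**Working it through.** The documents give no figure for this model. The stated sample size of 24 with about 80% power concerns the primary endpoint. It reproduces (16:8, SD 17.4, difference 20, two-sided 10%: power 82.3% by noncentral t) but has no bearing on this point.

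**1. Effect of unrecorded days.** With a constant daily rate r and d recorded days, the expected total is d × r, against 7 × r for a full week. The ratio is d/7.

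- d = 6: 6/7 = 0.857, a shortfall of 14%
- d = 5: 5/7 = 0.714, a shortfall of 29%
- d = 4: 4/7 = 0.571, a shortfall of 43%

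If both arms average the same d, the factor cancels from the arm ratio. If one arm averages 6 days and the other 7, a spurious ratio of 0.857 results with no treatment effect.

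**2. Short weeks built into the schedule.** Recording runs from Visit 1 (Day 0) to Visit 9 (Day 112), which is 113 days, or 16 weeks and 1 day. The model has 17 weekly totals, and 17 × 7 = 119 days. On the nominal schedule at least one week is therefore incomplete. If Week 0 is Days 0 to 6, Week 16 is Days 112 to 118 and holds one day. If Week 0 is Day 0 alone, it is the baseline that holds one day. The SAP does not say which.

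A shortfall common to everyone is absorbed by the week effect. Protocol 11, however, lets Visit 9 fall 7 days either side, from Day 105 to Day 119, which is 106 to 120 days of recording. Under the first definition, Week 16 then has anywhere from 0 to 7 days depending on the subject. A week effect cannot absorb that, nor a mid-week discontinuation.

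**3. Within-subject dispersion.** Let φ be the ratio of within-subject variance to mean. The documents give no value, so 1 to 3 is an assumed range. If the model fixes φ at 1, the true error of a nominal 5% one-degree-of-freedom within-subject contrast is 2 × [1 − Φ(1.96/√φ)]. For the 16-df treatment-by-week test, it is the probability that a chi-square on 16 df exceeds its own 95% point divided by φ.

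These were checked by simulation: 1,000 trials per setting, 16 and 8 subjects, 17 weeks, assumed mean of 10 or 20 movements per week, assumed between-subject SD of 0.4 on the log scale. The week-averaged test used each subject's 17-week total. True error in %; paired entries are mean 10 and mean 20:

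| φ | Change, Week 0 to 12 (formula) | Same (simulated) | 16-df interaction (formula) | Week-averaged treatment (simulated) | Week 12 arm difference (simulated) |
|---|---|---|---|---|---|
| 1 | 5.0 | 5.3; 6.1 | 5.0 | 6.0; 6.6 | 5.6; 4.8 |
| 1.5 | 11.0 | 9.4; 10.3 | 35.2 | 6.1; 4.3 | 6.6; 5.5 |
| 2 | 16.6 | 17.7; 15.5 | 66.2 | 5.0; 6.4 | 8.1; 7.0 |
| 3 | 25.8 | 27.2; 25.7 | 92.3 | 5.1; 6.0 | 13.3; 11.1 |

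The week-averaged test holds its level because the estimated subject variance takes up the extra variation in the totals. The arm difference at a single week lies in between.

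**The case against.** The best defence concerns dispersion. The equation contains a subject effect, which covers variation between subjects, and an error term by subject and week, which could carry variation within subjects. The part of the section that would say how that term is fitted is not readable here. The parallel CeD-GSRS section does survive: it has a residual term in the code, a choice of covariance structure by AIC, and a GEE fallback. SAP 8.6.1 also lets code be modified on statistical grounds without an amendment. A reader might infer from the Poisson sentence that the plan ignores extra-Poisson variation and that all its p-values for this endpoint are too small. The documents do not support that. The missing text cannot be held against the plan, and the week-averaged treatment test is not inflated in any case. This objection stands, and it reduces the dispersion point to a request for confirmation.

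On recorded days, the trial is double-blind and the documents give no reason to expect completion to differ by arm; equal under-recording cancels. Nor is a lower count always better, since SAP 8.6.2 also tabulates constipation. A reader might infer that under-recording favours AMG 714; nothing in the documents shows this. What remains is that the readable model has no exposure term, and the readable text has no rule for partial weeks and no definition of Weeks 0 and 16. With 8 subjects on placebo, a few short weeks could unbalance recorded days by chance.

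An offset is also imperfect. A blank day may be a true zero that was not documented, and a day with some entries may still omit a movement.

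**Conclusion.** The missing exposure term is a real gap in the readable plan. Weekly totals fall by about 14%, 29% or 43% with one, two or three unrecorded days, assuming a constant daily rate. The schedule itself produces short weeks whose length varies by subject. The between-arm bias equals the ratio of recorded days in the two arms and is nil when they match; its actual size is unknown.

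The dispersion point is conditional. It applies only if no within-subject dispersion is estimated and counts are over-dispersed; under-dispersed counts would make the within-subject tests conservative. Under that condition, the true error of change-from-Week-0 contrasts is about 11%, 17% or 26% for φ of 1.5, 2 or 3. The joint treatment-by-week test is affected more, and the week-averaged test is not.

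The consequence is limited to one secondary endpoint. The primary analysis does not use these counts, and the Go/No-Go rule in Protocol 13.1 rests on the two immunological responses.

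**What to change.** Before unblinding, add log(number of diary-recorded days in the week) as an offset in the count model. A day counts as recorded if it has at least one movement entered or is documented as having none. Treat a week with no recorded days as missing, not as zero. State which days make up Weeks 0 and 16, and how a week cut short by Visit 9 or discontinuation is handled.

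Also state how the subject-by-week error term is fitted: a residual scale, an observation-level random effect, or a negative binomial distribution. If the full SAP already does this, no change is needed on that point.

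The offset needs no new data and about one line of code. Its downside is that an undocumented zero day is treated as missing: with 5 recorded days and two true but undocumented zeros, the estimated rate is too high by a factor of 7/5 = 1.40. The currently planned analysis of raw totals can be kept as a sensitivity analysis, since it treats blank days as zeros. Estimating dispersion may widen confidence intervals for the week-specific contrasts.
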